b) Describe any animal experimentation and findings leading to the formulation of the study, if there is no supporting human data.

In oncology, whole-body PET/CT is typically performed from the head to the pelvic floor [7](eyes to thighs). The use of the term whole-body is misleading because the most commonly used field of view (FOV) for arms-up whole-body PET/CT protocols includes only the base of skull to the upper thighs and does not include the brain, skull, and large portions of both upper and lower extremities. In such FOV, the most commonly used site of injection, namely the antecubital fossa (inside of the elbow), is frequently not included in the imaging field. In the Frontiers in Oncology article, [name] also determined that based on the commonly used FOV at most PET/CT centers, that when infiltration is present, it may be unnoticed by clinicians in approximately 31% of the cases. (7) [See sources for citations on previous question]

Lucerno Dynamics, a privately held company in North Carolina, has also discovered that the static image may be incapable of reporting on the quality of FDG administration during the ~60 minute uptake period. Lucerno's system has been used in two investigational studies at two centers. At one center, the system was used with 8 patients for a total of 15 scans. At the other center, the system was used with 40 patients for a total of 85 scans. Similar rates of infiltrations were found to those described in the published articles. Based on this experience, Lucerno has found that infiltrations can partially resolve during the uptake period, so that even if they are visible in the PET image, the image may not reveal the extent of the infiltration. This could severely and negatively impact research and therapy decisions and thus patient outcomes.

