This study will determine if these time activity curves correspond to PET images of the injection site taken during the tracer uptake period. If time activity curves correspond to PET images, they can be used to determine if the tracer was properly injected. If there was an improper injection, clinicians can be alerted to this fact and interpret the image with this additional information.

Page numbers from a sponsor's protocol/grant may be referenced in 2b and 2c.

b) List your research objectives (specific aims & hypotheses of the study).

The study will try to answer the following questions:

- •How often do infiltrations of FDG occur in routine PET/CT imaging?
- •Can the Lucerno ID (sensor device) accurately determine the presence or absence of an extravasation as confirmed by PET imaging?
- •Can patterns be identified in the conditions that tend to lead to extravasation?
- •Is there a way to quantify the impact of an extravasation on the injected dose, and thus the SUV calculation?

Our hypothesis is that the Lucerno ID device accurately captures dose extravasations. Data extracted from Lucerno ID may help quantify extravasation and, in so doing, may allow for developing correction factors for measured SUV.

Please save frequently

c) Describe the study design (e.g., single/double blind, parallel, crossover, control, experimental, observational, etc.). If the study is investigator-initiated, a timeline for individual subject recruitment, follow-up, and analysis for the study is required. Also, indicate if the subjects will be randomized.

Investigator initiated, non blinded, experimental, non-randomized study

d) If subjects will be given placebo, please justify placebo use. *?HELP?*

N/A

3. Study Procedures

a) N Is this project a multicenter study (i.e., same project is conducted elsewhere by a different investigator) OR does this study involve conduct of research at multiple sites?
 Is SLU acting as a coordinating center for other sites OR is the SLU PI a direct recipient of a federal grant for this research? If yes, complete and attach the Supplemental

Protocol # 26741 [name]

Protocol Title: Patterns and Prevalence of FDG extravasation in PET/CT scans

Application for Coordinating Center Activities.

Will the SLU site be participating in all parts/procedures/arms of the study?

If No, explain what SLU will NOT participate in:

Please save frequently

Page numbers from a sponsor's protocol/grant may be referenced in 3b, 3c, and 3d.

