Once consent is obtained the patient will continue on with the standard of care screening process (name, DOB, height, weight, eating status, etc. will be obtained for the standard of care PET/CT exam). Lara Systems is planned for use once we get this system which is planned for the week of 10/17/2016. Our plan would be to still use the LD1 ID until we get the Lara device or as a back up if the Lara device is not working properly. Just before the radioactive FDG is injected, the four sensors (injection site, contralateral arm - similar position to injection site, liver, and over the subclavian area) on the Lucerno ID device will be placed on the subject by the PET/CT technologist. The device sensors will remain in place for the FDG uptake period (typically 60-90minutes). The patient will be lying on the scanning table or in a reclined chair for this uptake period, depending on the availability of the imaging table. During the uptake period, if the scanner and imaging table are available, the subject will have dynamic PET only images taken to correlate sensor data with imaging. This is not a necessary part of the protocol and will only be performed if the scanner is available. If the PET/CT scanner is not available, the sensors will be placed in the same locations and at the end of the uptake period, sensor only data will be retained. After the uptake time is complete, the sensors will be removed by the technologist and the patient will proceed on with their standard of care PET/CT imaging. The patient will not receive any extra radiation due to the study and should only add 5 minutes to the time of their PET/CT scan.

The study team will then upload the sensor data to a PC in the PET/CT department where it will be coded and sent to Lucerno Dynamics via a software for analysis. If requested, the coded PET data obtained during the uptake phase (no additional radiation involved with this imaging) will be complied and shared with Lucerno Dynamics. The patient will also be asked to complete a quick survey on the comfort of use for the Lucerno ID device. This coded paper survey will be shared with Lucerno Dynamics for further development of this device.

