c) If the proposed study is a clinical trial where a drug, vaccine, device or other treatment is compared to a placebo group or comparison treatment group, what are the guidelines or endpoints by which early decisions regarding efficacy or lack of efficacy can be made? For example, it may be reasonable to stop enrollment on a study when efficacy has already been

Protocol # 26741 [name]

Protocol Title:

Patterns and Prevalence of FDG extravasation in PET/CT scans

clearly demonstrated, to avoid unnecessary enrollments of additional subjects. Alternatively, it may be reasonable to stop enrollment when it is clear that efficacy will never be demonstrated, given the statistical power of the study as designed. Describe the guidelines that are in place to assist in making these determinations, if relevant to the proposed study.

This study does not include a control group, so there will be no comparison or efficacy measured.

d) Describe how data analysis will be performed (statistical tests, methods of evaluating data) and indicate the smallest group/unit for which separate reporting will occur. For studies involving a questionnaire, if data and reliability information are available, please describe or provide references. For full board, unfunded studies describe sample size determination and power analysis. If none, please justify.

The coded data (information will have study number only) will be reviewed by Lucerno Dynamics individually after each patient to look for quality. The quality will be reviewed to assess the injection site data visually and with time activity curves. Interval analysis will be done once significant recruitment has been achieved and reported if seen fit by SLU and Lucerno Dynamics. The data will be reviewed to look at group data and injection quality.

Please save frequently

- e) State if deception (including incomplete disclosure of study purpose/procedures) will be used. If so, describe the nature of the deception and provide a rationale for its use. Also, describe debriefing procedures or justify a waiver of the requirement to debrief. NOTE: for studies using deception, an alteration of consent must be justified in the Informed Consent section of the protocol (#13) and the debriefing script/statement must be uploaded in the Attachments section (#16). See IRB Deception Guidelines.

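### The device maker that analyses the sensor data may also obtain the uptake-phase PET on request, with no requirement that the sensor reading be recorded first

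*Protocol*

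**What the plan says.** One of the study questions in section 2(b) is whether the sensor can "accurately determine the presence or absence of an extravasation as confirmed by PET imaging". The sensor is therefore the test under evaluation and PET is the reference. Section 2(c) gives the design as "Investigator initiated, non blinded, experimental, non-randomized study".

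Section 3(b) describes the data flow. If the scanner is free during uptake, "the subject will have dynamic PET only images taken to correlate sensor data with imaging"; this imaging is optional. The study team uploads the sensor data to a departmental PC, "where it will be coded and sent to Lucerno Dynamics via a software for analysis". The next sentence opens with "If requested, the coded PET data obtained during the uptake phase" and provides for those images to be shared with the same company.

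Under section 3(d) the coded data "will be reviewed by Lucerno Dynamics individually after each patient to look for quality". That review of the injection site is partly visual and partly by time activity curve. Coding means that records carry a study number only.

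**The concern.** When a test is assessed against a reference, the test result should be fixed before whoever reads it can know the reference result. Otherwise a borderline reading can be settled, consciously or not, in the direction of the reference, and agreement then looks better than it is.

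Here the party that analyses the sensor data is the maker of the device, and the protocol lets it hold the PET as well. If infiltration calls were made or revised with PET in view, apparent sensitivity and specificity would tend to rise on the one aim that tests the device. Disagreements between sensor and PET are foreseeable: section 1(b) reports the maker's own finding that an infiltration can partly resolve during uptake, so that the image may understate it. Such cases invite reinterpretation.

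**Working it through.** No arithmetic applies. The protocol text available states no sample size, sensitivity, specificity or expected share of subjects with dynamic PET, so there is no figure to reproduce. The check is a reading of the sections side by side.

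1. **Is accuracy against PET an aim?** Yes. Section 2(b) asks the question and adds the hypothesis that the device captures extravasations accurately. Section 3(b) gives correlation with the sensor data as the purpose of the dynamic PET. The statement in section 3(c) that no comparison will be made answers a form question about control groups and early stopping; it does not withdraw the aim.

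2. **Who handles the sensor data?** The device maker: for analysis under 3(b), and in a patient-by-patient review under 3(d).

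3. **Can the same party hold the reference?** Yes, on request, under 3(b). The clause covers uptake-phase PET, which exists only when the scanner was free. It does not mention the standard-of-care PET/CT.

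4. **Can the two be linked within a subject?** This is an inference, but a firm one. The dynamic PET is taken on subjects wearing the sensors in order to relate the two records, and both are coded. A study number hides identity; it does not keep a subject's curve apart from that subject's images.

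5. **Is an order fixed?** No. Neither 3(b) nor 3(d) requires a sensor reading to be written down, dated or locked before PET is released, and neither names a sensor reader kept unaware of PET.

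6. **Is there room for judgement in the reading?** Yes. The review in 3(d) is partly visual, and no rule for turning a curve into a yes or no is given. Two devices are involved: under 3(b), Lara is to be used once it arrives, with LD1 until then and as back-up.

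Together, steps 2 to 6 show that a PET-informed sensor call is possible under the protocol as written. They do not show that one will be made.

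**The case against.** The strongest reply is that this rests on silence. Reading order and reader masking are often left to an analysis plan or reading manual, and the protocol never says that the maker issues the call used for the accuracy aim. Section 3(d) describes its review as one of quality. The curve itself is an instrument record that the site uploads and codes, and later sight of PET cannot alter it. Stored curves could be read again under a rule set without those images. The design label in 2(c) answers a standard form item and says little about how curves are read.

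Much of this stands. The label is weak evidence and the point does not depend on it. Only a judged call could move, not the counts, and a biased set of calls could be replaced by re-reading. What does not stand is that the matter is purely one for the analysis plan. The protocol itself sets the data flow, including release of PET without a timing condition, and that flow operates from the first subject. The quality review in 3(d) also concerns the injection site, which is where infiltration is judged.

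Two stronger readings should be resisted. A reader might infer selection bias from release being on request. That wording governs sharing with the maker; the protocol does not say that PET which is not requested drops out of the comparison. A reader might also infer that the PET reading is contaminated by the sensor curve. The protocol does not say how the PET is read in relation to the curve, and no such claim is made here.

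**Conclusion.** The concern holds as a matter of design worth considering, not as a demonstrated bias. The protocol allows an interested party to read the sensor with the reference available and does not require the reading to be recorded first. A reader might go further and infer that the maker will make its calls with PET in hand, or that the accuracy estimate is already compromised. The text supports neither: sharing is conditional, its timing relative to the sensor analysis is unstated, and it covers only the optional uptake-phase images.

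The direction of the risk is clear, towards better apparent agreement. Its size is not. It would depend on how many subjects have both records, how many are infiltrated and how often a call would be revised. The protocol gives published infiltration rates and scan counts from two earlier investigations, but no sample size for this comparison and nothing on revision, so any figure would be invented.

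The conclusion assumes that the accuracy aim will use a yes/no reading, as the wording of 2(b) implies, and that no step elsewhere fixes the order. The protocol text available ends in section 6 of the form, and no analysis plan was available.

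**What to change.** Amend sections 3(b) and 3(d) so that, for each subject with uptake-phase PET:

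- a dated yes/no infiltration call is recorded from the sensor data alone, by a rule written beforehand for the device used (LD1 or Lara);
- this is done before that subject's PET is released to the maker;
- the recorded call is the one used in the sensor-PET accuracy comparison;
- any later re-reading is labelled exploratory.

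No extra scans or subjects are needed. The maker waits a short time before it may use a subject's PET, and one dated record is added per subject. The larger cost is the call rule: none is stated, and one is needed for each device. A first rule may be provisional, provided that each call is dated under the version in force.

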The Lucerno devices (Lucerno ID) are nonsignificant risk devices that add only 2-3 minutes to the current standard of care PET/CT scanning process. Lucerno ID sensors are applied to the patient's skin before the injection of the radiotracer and are removed after the FDG uptake period and prior to the PET/CT imaging process. The Lucerno ID has the ability to identify infiltrations, whether they are within or outside the FOV of reviewing clinicians, and can alert clinicians before their patient undergoes a compromised PET/CT scan due to the infiltration. This technology can prevent patients from receiving the additional CT radiation exposure of a compromised scan, can save cost, and can improve patient outcomes by ensuring more accurate PET scan interpretation.

2. Purpose of the study

a) Provide a brief lay summary of the project in <200 words. The lay summary should be readily understandable to the general public.

PET (Positron Emission Tomography) images are used to help make patient management decisions in staging and treatment assessment, often after a cancer diagnosis.

Improper injections of PET tracers (dye) may occur approximately 15% of the time. This is known as extravasation or infiltration, and it compromises the doctor's ability to read the PET image. Often, the site where the tracer is injected into the vein (usually in the inside of the elbow) are not in the images taken, so reading physicians are unaware that an extravasation has occurred.

Protocol # 26741 [name]

Protocol Title: Patterns and Prevalence of FDG extravasation in PET/CT scans

Technology exists to capture time activity curves (amount of tracer in a location over a period of time) during the PET tracer uptake period (usually once the tracer is injected, the tracer circulates for 60 minutes prior to images), which can enable physicians to accurately detect extravasations. This information is currently unavailable to physicians reading routine PET/CT scans.

Time activity curves information gathered from these sensors during the circulation period appear to match the brief pictures taken approximately 70 minutes after the tracer injection.

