- f) Is there an accepted standard of care and/or standard practice at SLU for the condition/disease/situation being studied? This information will assist in comparing the risk/benefit ratio of study procedures relevant to usual care that would be received outside of the research context. *?HELP?*

If yes, please describe the standard of care and standard practice at SLU for the condition/disease/situation being studied.

g) Does this study involve any diagnostic imaging, labwork or genetic testing that could Y result in clinical discovery (diagnoses, genetic mutations, etc.)? Note that this could include discovery that is expected (related to the research) or incidental (not related to research aims, but possible, like a mass/shadow found in imaging despite not looking for it).

If yes, please describe and include whether there are plans to share findings with study participants.

This would be rare as these are additional images in the same location as the standard of care images; however, this is always a possibility with additional imaging. If something unexpected or unknown is discovered on the images, the reading physician will review with the Primary Investigator and inform the referring physician.

Protocol # 26741 [name]

Protocol Title:	Patterns and Prevalence of FDG extravasation in PET/CT scans	

Is this study subject to the NIH Genomic Data Sharing Policy? h)

Ν

The NIH GDS policy applies to all NIH-funded research that generates large-scale human genomic data as well as the use of these data for subsequent research and includes: genome-wide association studies (GWAS), single nucleotide polymorphisms (SNP) arrays, and genome sequence, transcriptomic, metagenomics, epigenomic and gene expression data, irrespective of NIH funding mechanism. Click here for more specific examples.

* * * Radioisotopes or Radiation Machines * * *

You have not selected the Radioisotopes option in the General Checklist. If you would like to add Radioisotopes information, please select the option to enable this section.

4. Radioisotopes or Radiation Machines

In this section, investigators must enter all radiation usage associated with the protocol.

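### Do sections 2(a) and 3(g) disagree on which body region the uptake-period PET images cover, so that the sensor loses its reference?

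*Protocol*

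**What the plan says.** The lay summary in section 2(a) gives the purpose: "This study will determine if these time activity curves correspond to PET images of the injection site taken during the tracer uptake period". Section 2(b) makes PET the reference for the device by asking whether the sensor can "accurately determine the presence or absence of an extravasation as confirmed by PET imaging".

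Section 3(b) describes the acquisition. If the scanner and table are free, "the subject will have dynamic PET only images taken to correlate sensor data with imaging". It adds: "This is not a necessary part of the protocol and will only be performed if the scanner is available". It names four sensor positions (injection site, the matching place on the other arm, liver, subclavian area) but gives no body region for the scan. Section 3(d) says of the data review: "The quality will be reviewed to assess the injection site data visually and with time activity curves".

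Section 3(g) asks whether study imaging could lead to a clinical discovery. The answer is that this would be rare, because "these are additional images in the same location as the standard of care images".

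On the usual field of view, section 1(b) says that the commonest injection site, "namely the antecubital fossa (inside of the elbow), is frequently not included in the imaging field". Section 2(a) says: "Often, the site where the tracer is injected into the vein (usually in the inside of the elbow) are not in the images taken".

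**The concern.** Section 2(a) places the uptake-period images at the injection site. Section 3(g) places them where the standard scan is taken, and the protocol's own case for the sensor is that the standard scan often misses the injection site. Location in 3(g) has to mean anatomy, because imaging in the same room or on the same scanner would be no reason to expect few new findings. So the two statements can hold together only where the standard field covers the injection site.

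If staff followed 3(g) and the standard field left the arm out, the dynamic PET could neither confirm nor exclude an infiltration in those subjects. The accuracy question in 2(b), and the question on quantifying the lost dose, would then have no reference there. Dynamic PET is optional, so the group with any uptake-period reference may be small to begin with.

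**Working it through.** The plan states no figure for this point, so there is none to reproduce. The check is a comparison of the sections, followed by a look at what the available numbers can support.

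**Which section governs the scan**

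- 2(a) states what the study will compare and names the injection site.
- 3(b) is the procedure. It gives the purpose of the dynamic scan, which is correlation with the sensors, and puts one of the four sensors at the injection site. Taken alone it leaves the region open, since the liver and subclavian sensors could also be correlated. Read with 2(a), it points to the injection site.
- 3(g) answers a question on incidental findings. It supports a claim of rarity and sets no field of view or table position.

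The feared loss therefore needs two things at once: that staff let 3(g) override the stated purpose, and that this centre's standard field omits the arm. The protocol shows neither.

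**What is known of this centre's field**

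Sections 1(b) and 2(a) describe general practice. No text available gives the field used here. Section 3(f), the natural place for it, shows no answer under its prompt, and other form fields are also blank in this copy, so the silence is weak evidence.

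The table in section 1 lists a retrospective series from the same university with 400 scans and 42 infiltrations (42/400 = 10.5%). Section 1(b) takes from an article in the same journal the figure that about 31% of infiltrations may go unnoticed under the common field. If that figure came from those 42 cases, which the protocol does not say, then 0.31 × 42 ≈ 13 infiltrations were known about although the common field could have missed them. That suggests images reaching beyond the common field. It makes agreement between 2(a) and 3(g) plausible but does not prove it.

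**What the numbers can support**

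Let p be the infiltration rate and f the share of infiltrations outside the field. Take p = 0.15 from 2(a), borrow f = 0.31 from 1(b), and assume 100 dynamic scans.

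- Infiltrations: 100 × 0.15 = 15.
- With a PET reference: 15 × (1 − 0.31) = 10.35. Without: 15 × 0.31 = 4.65.
- Widening of the confidence interval for sensitivity: 1/√(1 − f) = 1/√0.69 = 1.20. For f = 0.10 it is 1.05, and for f = 0.50 it is 1.41.
- If unimaged infiltrations were also scored PET negative, a perfect sensor would show specificity (1 − p)/((1 − p) + fp) = 0.85/0.8965 = 94.8%. For p = 0.03 it is 0.97/0.9793 = 99.1%, and for p = 0.21 it is 0.79/0.8551 = 92.4%. Positive predictive value would be 1 − f = 69%.

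The arithmetic is right, but the inputs do not measure this problem. The 31% concerns infiltrations that clinicians may not notice, and the protocol gives no number of dynamic scans. The last bullet depends on a scoring rule that appears nowhere in the protocol, and its predictive value only restates the assumed f.

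**The case for a change.** The best case for a change is that every reading leaves something to edit. If 2(a) governs and the standard field omits the site, the reason given to the ethics board in 3(g) is inaccurate, because a further region is being scanned. If 3(g) governs, the reference is lost in some subjects. If both hold, one sentence on this centre's field would say so. The region imaged is part of acquisition and belongs in 3(b), not in a statistical analysis plan. The standard scan may not stand in for the missing image, since section 1(b) reports that infiltrations can partly resolve during uptake. The edit would cost a line of text.

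Part of this stands. The wording does differ, the region imaged during uptake is not written down in 3(b), and the rarity argument in 3(g) would be too strong if the scan reaches beyond the standard field. But that last point concerns how the incidental-findings risk is described, and it does not affect the accuracy comparison. For the comparison, the missing line would only record a field that a team following 2(a) would use anyway. How to count a subject whose injection site was not imaged is a rule commonly left to the analysis plan, which is not at hand. That dynamic PET is optional is a separate feature of the design, true whichever region is scanned, and adds no weight here.

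**Conclusion.** No change to the plan is called for. Sections 2(a) and 3(g) are worded inconsistently, and a real conflict is possible but not shown, because this centre's standard field is not given in the text available. The stated purpose of the dynamic scan already directs it to the injection site, so a team carrying out the study would fill this gap sensibly.

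No defensible size can be put on the effect. The loss of about 4.7 in 15 infiltrations and the 20% wider interval are conditional illustrations, and the specificity and predictive-value figures rest on a scoring rule the protocol does not contain.

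The conclusion assumes that staff take the scan region from the study purpose and not from the incidental-findings answer. It would need another look if the centre in fact confined the dynamic scan to a standard field that leaves out the arm.
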